5.3 Concomitant Interventions

NHs will agree not to participate in other communication education programs during study involvement. Monitoring and technical assistance will be provided to each study site to ensure adherence.

5.4 Adherence Assessment

Monitoring of user statistics including: staff demographics, time spent in the modules, completion rate and program evaluation will be done by the Instructional Designer and her staff. Technical assistance including CHATO discussion boards will be provided by the Project Director and the Learning Systems Coordinator as necessary.

6 STUDY PROCEDURES

6.1 Schedule of Pilot Evaluations in NHs

Assessment	Initial Leadership Meeting	Treatment CHATO Planning (1 st Month)	Treatment CHATO Training (2 nd Month)	Treatment CHATO Follow-up (3 rd Month)	Closing Leadership Meeting	Final Data Collection
NH Agreement	X					
Staff CHATO Participation		X				
Staff Demographics			X			
Staff CHATO Knowledge Pre-Test			X			
Communication Rating Sheet Pre-Test			X			
Staff CHATO Knowledge Post-Test			X			
Communication Rating Sheet Post-Test			X			
Modified Duke Diffusion of Innovation Intention Survey			X			
Staff CHATO Evaluation			X			
Implementation Survey				X		
The Artifacts of Culture Change Tool				X		
Staff Wage Data					X	
NH Level Resident Data						X
Leadership Phone Interviews						X

6.2 Description of Evaluations

6.2.1 Screening and Randomization

Screening

For the R61, we partnered with seven Presbyterian Manor sites to pilot the CHATO intervention. These facilities have already been screened for eligibility and/or ineligibility. Letters of agreement will be collected from each NH as well as executive leaders from Presbyterian Manors. All staff at these sites will be invited to participate and will read and accept an exempt statement prior to taking the CHATO training.

Randomization

Randomization of pilot NHs will occur prior to any data collection. Those assigned to the pilot intervention group will receive the training first while the pilot control group is waitlisted. Randomization will occur by using a random number generator.

6.2.2 Consenting and Enrollment

Consenting Procedure

The project director will meet with NH leadership and obtain the Letter of Agreement at the initial leadership meeting at the start of the NH's assigned three-month intervention period. Signed Letters of Agreement will be stored electronically on a secure KUMC server. This procedure has been approved by the KUMC IRB.

Enrollment

Enrollment in the study begins with the initial leadership meeting and a signed letter of agreement from the participating NH. During the initial meeting, we will provide leadership and overview and implementation strategies as well as links to additional resources. We will also collect a list of staff emails. The training system will send the staff a link to the CHATO training and reminder emails.

- Initial Leadership Meeting
 - Letter of Agreement
 - List of staff and their emails that will participate in CHATO training

6.2.3 Treatment: CHATO Training

The treatment schedule may vary according to the needs of each individual nursing home; however, all modules will be completed by as many staff as possible during the three-month intervention period. Technical assistance will be provided as needed.

- Treatment: CHATO Training Module 1
 - Staff Demographics
 - Communication Rating Sheet Pre-Test
 - CHATO Knowledge Pre-Test
- Treatment: CHATO Training Module 2
- Treatment: CHATO Training Module 3
 - Communication Rating Sheet Post-Test
 - CHATO Post-Test
 - Modified Duke Diffusion of Innovation Intention Survey

- CHATO Program Evaluation

6.2.4 Completion and Final Evaluation

Competition

The NH's three-month intervention period will conclude with a closing leadership meeting that will include implementation strategies, challenges and successes, overall lessons learned, collection of surveys, and staff wage data.

- By Closing Leadership Meeting

- Implementation Survey
- The Artifacts of Culture Change Tool
- Staff Wage Data

If NHs need to discontinue study interventions early, circumstances and reasons will be documented. Discontinuation from the CHATO intervention is not anticipated, however, organizational confounds or special circumstances could interfere with participation rate.

Final Evaluation

Deidentified resident data will be provided by Presbyterian Manor for one-month prior to the training and one-month post. External evaluators will conduct leadership phone interviews following the closing leadership meeting. Interviews with leadership staff will provide insight into most effective implementation strategies and overall evaluation of the CHATO training process.

- Final Data Collection

- NH Level, Deidentified Resident Data from executive management
- Leadership Interviews by external evaluator

7 SAFETY ASSESSMENTS

7.1 Specification of Safety Parameters

This is a minimal risk pilot test of an online version of an educational program for nursing home staff that has been established as acceptable and effective. There are minimal risks for participants and participating in online continuing education is a regular job-related activity for nursing home staff. Participants may experience concern about their performance and ability to successfully complete the post-tests and about any sharing of performance-related data with their supervisor (only aggregate results that do not identify specific staff will be shared). Participants may experience frustration if they are challenged to navigate the online modules (only basic computer skills are required). Participants may experience some burden including the time and effort required to complete the online training modules, however this is limited to a 3-4 hour period.

CNA staff risks of participation include revealing CHATO training performance and survey responses to supervisory staff and administrators who may use this information for performance evaluations. Thus, NH administrators will not have access to data that identifies individual staff. Staff will be assured that descriptive data, CHATO performance, and survey responses will not be shared with administrators, supervisory staff, or other staff. In addition, recordings that may be used for future training materials or presentations will not identify the CNA or their NH employer. No appreciable risk of physical, psychological, social, legal or other harm to staff participants is expected. No information about past, present, or future physical or mental health or

payment of health care benefits (HIPAA protected information) will be collected.

Another potential risk is accidental disclosure of data outside the research team. Accordingly, all data will be handled as confidential by assigning codes, not including names, from the point of archiving through data analyses. The original data files and file linking data identification codes to participants will be stored in locked secure files or on secure KUMC servers. Data access will be controlled by the research protocol.

7.2 Methods and Timing for Assessing, Recording, and Analyzing Safety Parameters

Data Safety Monitoring Board (DSMB) will provide oversight to assure the safety of participants and integrity of the data. The members of the DSMB include a team of interdisciplinary professionals who are not a part of the research team. The DSMB members includes clinical and research experts on NH dementia care and NH staff education as well as a statistician.

The DSMB will meet twice yearly and additionally if needed at the request of the PI (due to issues arising in study conduct or major changes in study protocols). The DSMB will review reports of the research team concerning data quality and timeliness, adherence to study protocols, participant recruitment and accrual, and consenting procedures. The research team (under the direction of the PI) will report accrual, retention figures, and all adverse and other events and outcomes.

The Principal Investigator (PI) will be responsible for ensuring participants' safety daily and will monitor participant safety, evaluate progress of the study, and assure confidentiality, data management, and analysis. This includes continuous active review of research activities that will be completed with assistance of the Project Director (PD).

The PI will be responsible for submitting necessary reports (including minutes of annual and any additional DSMB meetings) to the funder. The PI will provide timely reporting of a) any unanticipated problems or unexpected adverse or serious adverse events that are determined to be related to the study protocol, b) IRB-approved revisions to the study protocol that indicate a change in risk for participants, c) a summary of recommendations made by the DSMB and if applicable the action plan for response, and d) notice of any actions taken by the IRB or regulatory bodies regarding the research and any responses to those actions.

To assure data control and safety for participants, each research team member will be trained and supervised by the site PI and/or PD, including instruction in all research activities, data handling, and in reporting subject complaints or other behaviors indicating a negative response to participation in the study immediately to the PI. Research team staff will be supervised during direct interactions with research study participants and provided with feedback.

All data identifiers will be removed for secured computer storage; a code will be assigned to each subject for data storage and the key linking the code number to subject identification will be kept secure by each site PI. All data will be deidentified prior to dissemination outside the research team.

7.3 Adverse Events and Serious Adverse Events

The OHRP Unanticipated Problem and AE Guidance definitions will be used for this study. Adverse Events (AE) will be documented on the Adverse Event Form and unanticipated events that are not adverse events will be recorded on the Unanticipated Problem form. Adverse events and unanticipated problems (Ups) will be reported to the IRB, DSMB and NIH Program Officer

as required. The PI will evaluate each AE for severity, whether it was expected or unexpected, and will determine relationship to participation in the study.

A Serious Adverse Event (SAE) occurs when an unanticipated event which may result in death, life threatening or places participant at risk of death, requires prolonged hospitalization, causes persistent or significant disability or incapacity, results in congenital anomalies or birth defects, or otherwise is judged to represent a significant hazard. SAE are not expected in this minimal risk exempt pilot study, however, the Principal Investigator (PI) will be responsible for ensuring participants' safety on a daily basis and will monitor participant safety.

7.4 Reporting Procedures

When SAEs occur that are unanticipated and are related to the intervention, they will be reported to the NIA Program Officer and to the DSMB Chair or designee, within 48 hours of the research team's knowledge.

Urs involving risks to study participants or others will be reported to the NIA program officer within 48 hours unless they are also SAEs

7.5 Follow-up for Adverse Events

A summary of all SAEs will be reported to the NIA Program Officer and to the DSMB quarterly.

7.6 Safety Monitoring

The DSMB will initially review and approve the written study protocol; data collection and storage protocols, intervention materials, informed consent procedures, and the plan for data and safety monitoring. Any outside agreements with vendors and subcontractors will be reviewed. The DSMB will also review the general reporting guidelines based on the study procedures approved by IRB. Reporting rules will be established taking into consideration the population under study and anticipated adverse outcomes (reflected in the human subjects' consent documents).

The DSMB will meet twice annually, either in-person or by teleconference call to review study progress, data quality, and participants safety. Safety reports are sent to the SO if necessary twice a year and will include a detailed analysis of study progress, data and safety issues. The content of the data and safety monitoring report will include: (e.g., study status, participant descriptive information, safety information, study quality). Blinded reports will be produced for open sessions and unblinded reports for closed sessions.

8 INTERVENTION DISCONTINUATION

This is a low risk study consisting of pilot testing an educational intervention. Thus, it is difficult to anticipate specific, a-priori stopping rules. If the research team, IRB, NIA program officer, and/or DSMB identify a pattern to these events, an interim analysis of safety data will be conducted to inform a decision for premature stoppage of study. Since this is a low-risk, short (six-month) pilot test of an educational intervention, no interim analyses on the primary study outcomes are planned.

9 STATISTICAL CONSIDERATIONS

9.1 General Design and Outcomes

Primary Objective

AIM 1. Establish acceptability and preliminary efficacy of online CHATO modules through pilot testing with NH staff.

Staff Outcomes: Knowledge gain and communication rating data will be compared between the intervention and wait-list control groups and within nursing homes before and after the CHATO training.

Resident Outcomes: The BPSD and medication reports will be provided for the one-month period before baseline data collection and for each month thereafter until the post-training assessment of the wait-listed nursing homes is completed (a total of seven months for both groups). Resident outcomes data will be compared between the intervention and wait-list control groups and within nursing homes before and after the CHATO training.

Secondary Objectives

AIM 2. Develop and pilot test the data collection tool with consultant input. Interviews of NH administrators and staff who participate in the pilot testing of CHATO and a process evaluation will be used to identify and develop supports for implementation and sustainability in preparation for future CHATO testing.

Implementation Outcomes: We will analyze NH strategies used to engage staff in CHATO (approach, motivation, incentives). Strategies will be described, categorized, and correlated with participation rates. A survey for CHATO group NHs, will describe how CHATO was implemented and concurrent activities that may have influenced BPSD and psychotropic use rates. The Artifacts of Culture Change Tool will describe the NH care environment and practices, leadership and workplace practices, staffing outcomes, and occupancy.¹⁰⁰ In addition, a simple cost-effectiveness analysis (CEA) for the cost associated with hypothesized BPSD reductions will be calculated.

9.2 Sample Size and Randomization

Seven NHs will be used to pilot the CHATO intervention during the R61. One nursing home will be used to test overall feasibility. The additional six will be randomized into three intervention and three waitlist controls using a random number generator. We estimate a CHATO training sample size of 150 participants.

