4.3 Study Enrollment Procedures

For the R61, we partnered with seven Presbyterian Manor sites to pilot the CHATO intervention. These facilities have already been screened for eligibility and/or ineligibility. Letters of agreement will be collected from each NH as well as executive leaders from Presbyterian Manors. All staff at these sites will be invited to participate and will read and accept an exempt statement prior to taking the CHATO training.

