The CHATO program is presented in three modules.^{37,63} Session 1 introduces effective versus ineffective communication. Participants identify communication issues in video vignettes. Session 2 focuses on identification and negative effects of elderspeak, using video-recorded

examples. Session 3 includes strategies for improved communication based on assessment of each resident's abilities. Participants critique communication in videos and correct transcripts to eliminate elderspeak. Training is limited to three, 1-hour sessions to assure feasibility in busy NHs. The modules include interactive exercises that must be successfully completed to advance through the program, assuring delivery of content fidelity and dose of the intervention. CHATO is provided to as many staff as possible to achieve facility-wide effects of reduced elderspeak.⁶⁷

NH sites will receive the link to the trainings in three-month intervals according to the randomization plan. The NH leadership will determine the best method of implementation for their site. The link to the training will be shared with staff and the staff will have three months to complete all three modules. The modules contain pre and posttests (scenario-based questions and rating of staff communication in video clips) to evaluate knowledge gain from CHATO. The Modified Duke Diffusion of Innovation⁵⁸ survey provides information about CHATO participant intentions to use learned skills in practice and the likelihood for translation.

During the R61, the instructional designer will assure that data for identifying each participant's NH and metrics including time spent in each module are collected for analyses.^{34,37}

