9.4 Data Analyses

SAS software⁷¹ will be used for all analyses. Initial analysis will calculate descriptive statistics at

all data collection points. Outliers will be investigated for accuracy and possible entry errors. Graphic representation of data and correlations among variables will be examined. Patterns and site effects of missing data will be examined in relation to variables of interest.⁷²

Knowledge gain and communication rating data will be compared between the intervention and wait-list control groups and within nursing homes before and after the CHATO training. Changes in knowledge from Time 1 (baseline) to Time 2 will be compared between immediate and wait-listed groups using model estimates obtained with a linear mixed model (LMM) approach to account for repeated measures and clustering within nursing homes. Next, pre- to post-training changes in knowledge will be combined for immediate and wait-list groups and also tested using LMM approach. The models will be adjusted for covariates, such as staff role (RN, LPN, CNA, other), experience, and whether the nursing home has a SCU or not. Distributions of residuals will be evaluated for normality and variance homogeneity and variables will be transformed as needed or statistical analyses for non-normal data will be utilized.

The BPSD and medication reports will be provided for the one-month period before baseline data collection and for each month thereafter until the post-training assessment of the wait-listed nursing homes is completed (a total of seven months for both groups). Resident outcomes data will be compared between the intervention and wait-list control groups and within nursing homes before and after the CHATO training. Seven months of data will be plotted to examine changes in nursing homes and resident outcomes.

We will analyze NH strategies used to engage staff in CHATO (approach, motivation, incentives). Strategies will be described, categorized, and correlated with participation rates. A survey for CHATO group NHs, will describe how CHATO was implemented and concurrent activities that may have influenced BPSD and psychotropic use rates. The Artifacts of Culture Change Tool will describe the NH care environment and practices, leadership and workplace practices, staffing outcomes, and occupancy.¹⁰⁰ In addition, a simple cost-effectiveness analysis (CEA) for the cost associated with hypothesized BPSD reductions will be calculated.

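### Six homes are randomised 3:3 with no restriction on SCU status, the one home-level covariate named, so a chance draw can confound SCU with arm; the damage depends on an unstated SCU count and model form

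*Combined protocol and SAP*

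**What the plan says.** Section 9.2 allocates the homes in one sentence: "The additional six will be randomized into three intervention and three waitlist controls using a random number generator". Section 6.2.1 repeats the method: "Randomization will occur by using a random number generator". Section 5.1 refers to a randomisation plan ("NH sites will receive the link to the trainings in three-month intervals according to the randomization plan"), but its content is not given. No stratification, matching or constraint appears in the text.

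For the primary outcome, Section 9.4 sets the comparison as follows: "Changes in knowledge from Time 1 (baseline) to Time 2 will be compared between immediate and wait-listed groups". The method is a mixed model that allows for repeated measurements on staff and for homes as clusters. Adjustment for covariates is added, with three examples: the staff member's role, their experience, and SCU status, which is worded as "whether the nursing home has a SCU or not". Section 3 says the same. Role and experience belong to the staff member, so SCU status (taken here to mean a special care unit) is the only home-level covariate named. The text does not say whether SCU enters as a main effect, interacts with time, or is fitted to change scores. It does not say how many homes have an SCU.

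Resident behavioural and medication outcomes are also compared between arms (Sections 3, 9.1 and 9.4), with no adjusted model described.

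**The concern.** The plan intends to adjust afterwards for a home-level factor that it could balance beforehand. Six homes split 3:3 allow only 20 allocations, so severe imbalance is not remote. If SCU and arm coincide, or nearly do, the randomised comparison of knowledge change becomes hard to interpret: either the model cannot separate the two factors, or it silently credits one to the other. The resident comparisons carry the same risk without any stated adjustment.

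**Working it through.** **Inputs.** Six homes, 3:3 (Section 9.2); SCU as a binary home-level covariate (Section 9.4). The number k of SCU homes is not stated, so every value from 0 to 6 is taken. The plan gives no power, effect size or intracluster correlation, so there is no figure of its own to reproduce.

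**1. Draws.** There are C(6,3) = 20 equally likely allocations.
- k = 3: all three SCU homes fall in the same arm in 2 draws, 2/20 = 10%.
- k = 2: both SCU homes fall in the same arm in 2 × C(4,1) = 8 draws, 8/20 = 40%. For k = 4 the same count applies to the two non-SCU homes.

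**2. If SCU adjusts the change** (change-score model, or SCU × time in the mixed model). With equal precision per home, the variance of the arm effect relative to a model without SCU is 1/(1 − φ²), where φ is the arm–SCU correlation.
- k = 3, split 2:1: φ = (2×2 − 1×1)/9 = 1/3, ratio 1/(1 − 1/9) = 1.125.
- k = 2, split 2:0: covariance 2/6 − (1/2)(1/3) = 1/6; variances 1/4 and 2/9; φ² = (1/36)/(1/18) = 1/2, ratio 2.0.
- k = 1: covariance 1/6 − 1/12 = 1/12; variances 1/4 and 5/36; φ² = 1/5, ratio 1.25.

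| SCU homes (k) | Result over the 20 draws |
|---|---|
| 0 or 6 | no effect |
| 1 or 5 | 1.25 in all 20 |
| 2 or 4 | 2.0 in 8; 1.0 in 12 |
| 3 | inestimable in 2; 1.125 in 18 |

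Fitting SCU also reduces the home-level degrees of freedom from 6 − 2 = 4 to 3, and the two-sided 5% critical t rises from 2.776 to 3.182. At ratio 2.0 the 95% interval is √2 × 3.182/2.776 = 1.62 times as wide as without SCU. With unequal home sizes and some missing Time 2 data, the 2.0 became 1.92.

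**3. If SCU is a main effect only.** Write the mean as β0 + β1·t + β2·A + β3·A·t + γ·S, with A for arm, S for SCU and t = 0 or 1. The expected change is β1 + β3·A, so S cancels. A generalised least squares check used 25 staff per home (150/6) and assumed variance components of 0.05 for home, 0.03 for home × time, 0.45 for staff and 0.47 for residual. The arm × time contrast was estimable in every SCU split checked, at variance ratio 1.00, including the fully confounded one. If both arms are forced to share a baseline mean, the ratio was about 1.23 to 1.26 in the fully confounded draw and 1.10 to 1.12 in the 2:0 draw.

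That model does not adjust the change for SCU. Suppose SCU homes change by δ more than non-SCU homes for reasons other than training. For a given draw, and equal home sizes, the contrast is shifted by δ × (share of SCU homes in the immediate arm − share in the wait-list arm). The size of the shift is δ for 3:0, (2/3)δ for 2:0 or 3:1, (1/3)δ for 2:1 or 1:0, and 0 for 1:1.

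**4. With a limit of one on the difference in SCU homes.** For k = 3, 18 of 20 allocations remain (ratio 1.125, shift at most δ/3). For k = 2 or 4, 12 of 20 remain (ratio 1.0, no shift). For k = 0, 1, 5 or 6, all 20 remain and nothing changes.

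**The case against.** The strongest reply is that Section 9.4 names a repeated-measures mixed model, and the ordinary reading of covariate adjustment there is a main effect. A covariate that does not vary over time then drops out of the comparison of changes, and no degree of freedom is lost from that contrast. This stands. A reader might infer that the planned model cannot estimate the arm effect after a bad draw; the documents do not support that as a general statement, because they leave the form of adjustment open. What the reply does not remove is the confounding itself: the main-effect model leaves SCU-related differences in change in the arm effect.

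Three further points stand:
- A reader might infer that the knowledge contrast is the only randomised evidence in the pilot. It is not; communication ratings and resident outcomes are also compared by arm.
- Section 4.3 says "These facilities have already been screened for eligibility and/or ineligibility", but the eligibility criteria do not mention SCU status and Table 5 describes no form that records it. It cannot be assumed to be already on file.
- The covariates are given as examples, so SCU could be dropped. No rule says when, so dropping it after a bad draw would be a post hoc choice.

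Finally, unrestricted 3:3 randomisation is valid: averaged over all draws it is unbiased, and this is a pilot with no power claim. That limits the importance of the point, but a single draw of six homes is what will be analysed.

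**Conclusion.** The point holds in a conditional form and is minor. The allocation leaves the one named home-level covariate unrestricted. With 2, 3 or 4 SCU homes among the six, there is a 40%, 10% or 40% chance, respectively, of a draw that aligns SCU with arm as far as that count allows. Inestimability (k = 3), doubled variance (k = 2 or 4) and the fall from 4 to 3 degrees of freedom follow only if SCU adjusts the change itself; the factor 2.0 assumes equal precision per home. If SCU is a main effect only, precision is unaffected, and the cost is unadjusted confounding of up to the full SCU-related difference in change. The resident comparisons are exposed in the same way. Inestimability and doubling need different SCU counts, so they are alternatives and not joint risks. With 0, 1, 5 or 6 SCU homes, restricting the draw has nothing to offer. The SCU count and the model form are the two facts that decide the size of the problem, and the documents give neither.

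**What to change.** In Sections 9.2 and 6.2.1, record the SCU status of the six homes before the draw, report the count, and select at random among only those 3:3 allocations in which the number of SCU homes differs between arms by at most one.

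In Section 9.4, state how SCU enters the model for change: main effect only, SCU × time, or covariate in a change-score model. Note that a main effect alone does not adjust the change.

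The cost is one piece of information per home obtained before randomisation, one condition in the allocation program, and a sentence or two in each section. The downside is fewer allocations when k is 2, 3 or 4. If a randomisation test were used (the plan specifies none), its smallest two-sided p-value would rise from 2/20 = 0.10 to 2/18 = 0.11 (k = 3) or 2/12 = 0.17 (k = 2 or 4).
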